#### 1 - GENERAL STUDY INFORMATION

#### 1.1 INTRODUCTION

There is surge in COVID infected patients in New York City with a shortage of hospital beds, ICU beds and ventilators. Strategies to reduce the need for all of the above are immediately needed. Further, few interventions are targeted in COVID infected patients early in the course of their disease and especially in the community/home settings. Respiratory decompensation appears to occur later in the disease process (i.e. 7-10 days after becoming symptomatic) therefore many patients are sent home from the Emergency Room only to decompensate later at home. Some patients die at home and others are returning to the Emergency Room with advanced hypoxemic respiratory failure. There is no treatment offered to this population of patients, i.e. COVID suspected or confirmed and with respiratory symptoms or abnormal chest x-ray at the time of presentation. Based on experience across the globe, these patients are likely to worsen at home. We therefore propose a prospective, single-center, parallel group, open-label, randomized clinical trial to assess the efficacy of continuous positive airway pressure therapy (CPAP) (FDA approved and often used for treatment of sleep apnea) in COVID confirmed or suspected patients with abnormal chest x-ray or respiratory symptoms who do not require hospital admission and are discharged home from the emergency room. CPAP delivers positive pressure ventilation through a noninvasive facemask and can therefore be used at home. There is limited evidence on the use of CPAP for viral pneumonia resulting in acute respiratory distress syndrome (ARDS), as it offers no clear advantage over mechanical ventilation. However, in the last two decades, two viral pandemics (SARS 2003 and H1N1 2009) have triggered investigation into the use of CPAP due to severe shortage of mechanical ventilators. The success rate of CPAP was as high as 84% in H1N1 infected hospitalized individuals with lower severity of illness. Further, CPAP use in COVID-infected patients with respiratory abnormalities has shown promise in other countries such as England, China and Italy.

#### 1.2 DESIGN AND OBJECTIVES

#### STUDY DESIGN

This is a prospective, single-center, parallel group, open-label, randomized clinical trial, where we will investigate the efficacy of continuous positive airway pressure therapy (CPAP) in COVID suspected or confirmed patients who are sent home from the emergency room with mild pneumonia or respiratory illness but who do not require hospital admission. We propose a randomized controlled trial of CPAP (n=100) vs. control (n=100) in COVID-19 suspected or confirmed patients with pneumonia or respiratory illness. The overarching aim of this proposal is to determine if early use of CPAP at home will reduce the need for hospitalization or death in COVID-19 suspected or confirmed patients. We will include adult patients (age>18), oversampling when possible for obese patients who live alone or have more than one bedroom at home, with serologically confirmed or under investigation for acute COVID-19 infection, who have one or more of the following: fever (>38°C), sore throat, myalgia or flu-like illness AND have one or more of the following additional symptom or diagnostic criteria: abnormal chest xray, new onset cough, mild hypoxemia at rest (saturation less than 96%), abnormal lung exam, chest tightness or shortness of breath AND who are without need for hospital admission. Patients with preexisting pulmonary diseases such as advanced COPD, advanced parenchymal lung disease, history of pneumothorax etc. will be excluded (see inclusion and exclusion criteria for more information). Participants in both arms will be shipped a pulse oximeter to monitor oxygen

saturation and a disposable home sleep apnea monitor (WatchPAT) to track blood oxygen level continuously for 12 hours with data feed into a cloud based platform. Additionally, 100 patients will be randomized to receive CPAP at fixed pressure of 8 cm in women and 10cm in men and obese men and women will start be set at 10cm. of water pressure for 72 hours continuously (except for daily activities such as eating, grooming etc). We will adjust pressures in the range of 8-10cm depending on patient's comfort and related assessments in follow up period. However, the range of the pressure will remain constant throughout the study. While the study protocol will end at 72 hours, patients who wish to continue CPAP will be allowed to do so for symptomatic benefit up to 7 days from randomization. All CPAP recipients will be given a full-face mask and will be asked to stay in quarantine for the duration of the protocol to avoid risk of infecting family members with aerosol (information on this presented below). We hypothesize that early CPAP in COVID infected patients who have respiratory abnormalities will decrease the risk of subsequent hospitalization or death in 14 days from randomization.

#### **OBJECTIVES**

Aim 1: Given the expected shortage of ventilators to treat COVID-19 suspected or confirmed individuals with severe acute respiratory distress syndrome (SARS)/ARDS, we propose a prospective, single-center, parallel group, open label, randomized clinical trial of CPAP (n=100) vs. control (n=100) in COVID-19 suspected or confirmed patients with abnormal chest x-ray or respiratory symptoms. The overarching aim of this proposal is to determine if early use of CPAP at home reduces the need for hospitalization admission or death in COVID-19 suspected or confirmed patients. We will include adult patients (age>18), oversampling when possible for obese patients who live alone or have more than one bedroom at home, with serologically confirmed or under investigation for acute COVID-19 infection, who have one or more of the following: fever (>38°C), sore throat, myalgia or flu-like illness AND have one or more of the following additional symptom or diagnostic criteria: abnormal chest x-ray, new onset cough, mild hypoxemia at rest (saturation less than 96%), abnormal lung exam, chest tightness or shortness of breath AND who are without need for hospital admission, i.e. being sent home. Patients with preexisting pulmonary diseases such as advanced COPD, advanced parenchymal lung disease, history of pneumothorax etc. will be excluded (see inclusion and exclusion criteria for more information). Participants in both arms will be shipped a pulse oximeter to monitor oxygen saturation and a disposable home sleep apnea monitor (WatchPAT) to track blood oxygen level continuously for 12 hours with data feed into a cloud based platform. Additionally, patients in the treatment arm (n=100) will be randomized to receive CPAP at fixed pressure: 8 cm water pressure in women and 10cm water pressure in men. All obese patients (BMI>=30) will be treated with a fixed pressure of 10cm of water pressure (both men and women). The CPAP pressure will be adjusted based on patient's comfort but will not deviate from the range of 8-10cm noted above. The treatment will be prescribed for 72 hours continuously (except for daily activities such as eating, grooming etc). While the study protocol will end at 72 hours, patients who wish to continue CPAP will be allowed to do so for symptomatic benefit up to 7 days. All CPAP recipients will be given a full-face mask and will be asked to stay in quarantine for the duration of the protocol to avoid risk of infecting family members with aerosol. We hypothesize that initiation of early CPAP in COVID infected patients with respiratory abnormalities will decrease the risk of subsequent hospitalization or death in 14 days from randomization. Patients will be followed for 28 days and as a secondary endpoint we will assess 28 day mortality as well as to assess for late impact of CPAP.

Aim 2: Younger Americans with COVID-19 infection have a higher rate of hospitalization and need for mechanical ventilation compared to younger citizens of other countries. One potential explanation is high obesity prevalence. Obstructive sleep apnea is present in over 50% of obese individuals and obesity further compromises lung compliance and ability to handle increased ventilatory demand seen in COVID-19 patients with related lung injury. Further, COVID infected individuals with OSA may be at higher risk for progression from mild pneumonia to ARDS however this remains to be determined. Therefore in Aim 2, we will determine if obstructive sleep apnea (OSA) is associated with increased hospitalizations and mechanical ventilation in COVID-19 suspected or confirmed patients. This will be achieved primarily through our control group (not receiving PAP therapy but will receive home sleep apnea testing). This is of vital importance as the primary treatment of OSA is CPAP and there are more than 8 million CPAP users in the United States. This treatment can therefore be leveraged to treat mild respiratory distress in COVID infected OSA patients in the face of a crisis with hospital and ventilator shortage. We hypothesize that obese patients with COVID-19 infection are more likely to be hospitalized or receive mechanical ventilation compared to non-obese individuals with COVID-19 infection. In exploratory analysis, we will also assess if OSA is an independent risk factor for hospital admission or death in our control group. We expect obesity and OSA to be correlated and will determine the independent impact of each of these on our primary endpoint.

**Aim 3:** To leverage EHR to determine a risk score to predict readmission to the Emergency room in COVID-infected or suspected patients. This aim will be done simultaneously while Aims 1 and 2 are ongoing and will be implemented in real-time to identify high-risk patients.

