#### 7.1 VISIT SCHEDULE

#### Study Procedures:

- 1) Patients will be screened as described earlier
- 2) Eligible patients will be provided a flyer by ED provider when possible but may also be contacted by telephone once they have been discharged. (Of note: we are being approached by patients who are discharged from the hospital with COVID pneumonia who continue to experience shortness of breath and are requesting a CPAP without having prior knowledge of this study).
- 3) Research will be introduced to the patient, and if they agree to participate, a telephone consent will be conducted (according to IRB requirements including witness). Once patients have enrolled in the study, their PMD will also be notified of their participation. The patient will also be added to the study on EPIC, so that all treating physicians are aware of the patient's participation in our study.
- 4) Once patients have enrolled in the study, a pulse oximeter and a disposable WatchPAT One device will be mailed to the patients (within 24-48 hours of discharge). Orders placed before noon will be delivered the same day by a local durable medical equipment company we are working with. Orders placed past noon, CPAP delivery will be done the subsequent day or upto 48 hours if outside the New York area. Patients who are randomized to the treatment arm will receive a CPAP machine and three full-face masks in addition to the above noted equipment.
- 5) Patient will then be instructed via facetime or other video platform on CPAP setup and use, face mask fitting (those randomized to CPAP), and use of the WatchPAT One and pulse oximeter (for both CPAP and control arm). All participants will wear the WatchPAT one for one night whereas the oximeter will stay on continuously and the patient will report the saturation to us via follow up survey.
- 6) Patients randomized to receive CPAP will be asked to stay in isolation throughout the duration of the study i.e. 72 hours. They will be required to stay in a different room with the door shut and windows open (weather permitting). We will also ask the patient to stop using CPAP during meals or other daily activities. Subjects not on CPAP machine will also be instructed to sleep in a room with windows open (weather permitting).
- 7) Patients will use the CPAP machine as instructed for 72 hours.

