- 8) All patients will be contacted every 6-12 hours to complete follow up assessments. These follow ups will be done via a phone call. If the timing of these follow ups fall between 10pm-6am, the follow up will be deferred until after 6am. After 72 hours, all patients will then be contacted daily until day 14 from randomization. After day 14, research staff will continue to monitor the medical charts for any visits to the hospital. One last contact will be made on day 28.
- 9) After 72 hours, patients will be asked to discontinue using the CPAP and pulse oximeter. If patients wish to continue to use the CPAP, they may do so for up to 7 days from time of randomization.
- 10) The research staff will continue to call all patients daily (after the 72 hour mark) to assess symptoms.
- 11) The patients can also choose to monitor their oxygen saturation beyond the 72 hours of treatment.
- 12) CPAP download is available continuously however we will download data on usage, pressure, leak daily and make adjustments to the mask or CPAP pressure as needed for patient comfort. For patients experiencing significant trouble tolerating high pressure, we will decrease CPAP from 8-10 cm to a fixed CPAP of 5 cm for 2-4 hours after which we will raise it back to 8-10cm for the

- duration of the study. If the patient is not able to tolerate the pressure again, we will reduce it back to 5cm of water pressure for several hours before increasing the pressure. This will be continued until the patient withdraws or 72 hours are completed, whichever occurs first.
- 13) Patients will be asked to track their own oxygen saturation using the provided pulse oximeter and report it when we contact them for the 6-12 hour follow up calls/surveys.
- 14) The sleep apnea test will provide continuous oxygen and breathing data for a period of 12 hours during the 72 hours and will also provide information on oxygen saturation while the patient is asleep.

The outline of the forms that correspond to the study visits can be found in the Appendix, Figure 1. All of these forms are subsequently included in the following appendicies.

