#### SCREENING VISIT

Upon reaching out to patient, the coordinator will confirm enrollment eligibility with the patient prior to consenting.

#### 7.3 VISIT 1

Visit 1 is performed by the coordinator. It consists of the following forms:

- Phone consent
- Enrollment Eligibility Form
- ER Admission Data Form
- Demographics and Subject History Form
- Participant Contact Form
- Medications Form
- CPAP and WatchPAT Assignment Form
- PROMIS questionnaire Form
- Randomization Form
- Respiratory Questionnaire Form
- 1. Once the Mount Sinai team has randomized patient, we will email [contact] with demographics and equipment ordered.
- 2. Community surgical will call patient to confirm address and information, they will then initialize the WatchPAT.
- 3. The pin used will be the DOB in the following format: MMDD
- 4. The pin will be written on the WatchPAT box as well
- 5. Community surgical will then deliver the equipment box to the patient. Patient will receive documents to sign via docusign.

- 6. Once delivery has been made, community surgical will notify PI
- 7. Community surgical will register patient on encoreanywhere once patient has been registered it will take approximately 24 hours before we are able to see the patient on our end

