## **Enrollment Eligibility Form:**

## **ER Admission Data Form**

*This is abstracted from the chart, data from the date of their admission to the ER prior to baseline
1. Date of admission to the ER:
2. Time of admission to the ER:
3. Number of days since symptom onset:
4. Source of COVID infection:

□ Unknown

□ Known

□ Occupational

□ Household
□ Other:
5. Did patient have any of the following symptoms (y/n):    Fever (y/n)   Cough (y/n)   Shortness of breath (y/n)   Chest tightness (y/n)   Sputum (y/n)   Nasal congestion (y/n)   Sore throat (y/n)   Chills (y/n)   gastrointestinal symptoms (y/n)
Vital signs in the ED
6. Temperature Fahrenheit:
7. Oxygen saturation:
□ Without supplemental oxygen
□ With supplemental oxygen
☐ How much supplemental oxygen?
☐ What method of oxygen: nasal canula, face mask, high flow nasal canula
8. Blood pressure:/
9. Pulse:

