Proportion of patients with Negative outcome	Control	0.25	0.30	0.35	0.4	0.45	0.5
	СРАР	0.09	0.12	0.16	0.20	0.25	0.29
	Relative reduction in CPAP arm (%)	64	60	54	50	44	42

Randomization Design and Procedure

Patients will be randomized using a 1:1 allocation to CPAP versus control group. The randomization will be stratified by BMI ($\geq=30$ and ≤30), gender and age (≤60 , $\geq=60$). A random permuted block design will be employed, with random blocks of size 2 and 4.

Data Monitoring and Analysis

Primary Efficacy Analysis

The primary efficacy endpoint is the proportion of patients with a negative composite endpoint within 14 days of randomization and will be compared between CPAP and control groups. The null hypothesis is that the proportion of patients with a negative outcome will be the same between patients randomized to CPAP versus control arm. This hypothesis will be tested using a two-sided Fisher's exact test at 0.05 alpha level. The primary analysis will be conducted according to the intention-to-treat principle.

Early stopping rule: If three deaths are observed in the CPAP group, enrollment will be halted pending DSMB review and recommendations. As of April 03, the death rate for COVID-19 positive patients in NYC was 2.99% [95% Clopper Pearson CI= 2.986, 2.997]. The rate is expected to be lower for our patient population. As such, 3 deaths among 100 patients will indicate a proportion of 3% [95% CI: 2.57%, 3.78%].

Analyses of Secondary Endpoints

Safety

Safety analyses will be conducted according to randomization assignment and treatment actually received. Adverse event rates will be calculated as the ratio of the total number of events over 14 days divided by total patient-days at risk for the specific event from randomization. A Poisson model with robust variance estimation will be used to compare SAEs between CPAP and control patients.

Time-to-events outcomes

Time from randomization to event outcomes (Hospitalization or ED visit, ICU admission, intubation and mechanical ventilation) within 14 days of randomization will be compared between randomization groups using a log-rank test or Gray's test in the presence of competing risk of death. In addition, survival at days 14 and 28 post-randomization will be described by Kaplan-Meier curves and a log-rank test will be used to compare survival between the two groups.

Respiratory Function

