- Improvement in oxygen saturation will be compared between randomization groups using linear mixed-effect models with patient as a random effect.
- Improvement in respiratory symptoms, as measured by the Clinical COPD Questionnaire, will be compared between randomization groups using linear mixed-effect models with patient as a random effect.

Conversion rate of family members

The conversion rates (yes/no) of family members in the two randomization groups will be compared using a Fisher's exact test. If there is sufficient variability, a zero-inflated count model may be considered as well.

Continuation of CPAP for greater than 72 hours

The proportion of patients in the CPAP group who elected to continue CPAP use after 72 hours will be estimated along with 95% Coppler-Pearson confidence intervals.

Exploratory Analyses

Exploratory analyses will be conducted similarly as the primary analysis except that it will be only in the control arm comparing OSA versus non-OSA patents and obese vs non-obese patients.

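### Aim 2 promises the independent effect of OSA, but the SAP tests OSA unadjusted, from a single night recorded after randomization during acute COVID

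*Protocol*

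**What the plan says.** **The aim.** Protocol section 1.2, Aim 2, asks whether OSA goes with more hospitalization and ventilation: "This will be achieved primarily through our control group (not receiving PAP therapy but will receive home sleep apnea testing"). It adds an exploratory question, whether OSA is an independent risk factor for admission or death in controls. It expects OSA and obesity to be correlated and undertakes to find the independent effect of each on the primary endpoint.

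**The exposure.** Section 7.1 provides one recording: "All participants will wear the WatchPAT one for one night whereas the oximeter will stay on continuously". On timing: "The sleep apnea test will provide continuous oxygen and breathing data for a period of 12 hours during the 72 hours". The device is ordered after allocation: section 7.3 says "Once the Mount Sinai team has randomized patient, we will email" the equipment order. Section 7.1 states that "a pulse oximeter and a disposable WatchPAT One device will be mailed to the patients (within 24-48 hours of discharge"), with same-day delivery for orders placed before noon.

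**The outcome and test.** In the SAP, "The primary efficacy endpoint is the proportion of patients with a negative composite endpoint within 14 days of randomization", compared by a two-sided Fisher's exact test at 0.05. For OSA the SAP says only: "Exploratory analyses will be conducted similarly as the primary analysis", restricted to controls, comparing OSA with non-OSA and obese with non-obese patients.

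**What is not given.** The documents state no OSA threshold, no model for the independent effects, and no rule for controls without a valid recording. The SAP's missing-data rule covers a missing primary outcome only.

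**The concern.** There are two separate problems.

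First, the method does not match the aim. A two-by-two table gives a crude association. It cannot say whether OSA matters beyond obesity, although the Protocol itself expects the two to go together.

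Second, the exposure is read from oxygen and breathing signals in people who entered the trial because of acute respiratory illness. If worse lung disease disturbs those signals, sicker patients will more often be labelled OSA, and they are also more likely to be admitted. An association could then appear with no effect of OSA at all. Limiting the outcome to admission, ventilation or death would not cure this, because the exposure is what is affected.

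The stake is interpretation. Aim 2 presents OSA as a reason to direct CPAP to these patients. A crude association that partly reflects how ill someone was that night could be read as support for that.

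**Working it through.** **1. The plan's own figures.** The SAP gives no power statement for OSA. Its table concerns CPAP against control, 100 per arm. Exact enumeration of the two-sided Fisher test gives power of 0.83, 0.85, 0.84, 0.84, 0.81 and 0.83 for the six columns, so the stated power above 80% is reproduced. The OSA comparison splits one arm of 100. With an assumed 50/50 split and a 25% event rate, a doubled risk (33% against 17%) has power 0.41.

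**2. Severity acting on both label and outcome.** Inputs from the SAP: 100 controls, and event rates of 25% and 40% from its 25-50% range. Everything else is assumed:
- severity S ~ N(0,1)
- sleep index I = ρS + √(1−ρ²)·e, with ρ = 0.3 or 0.5
- OSA = I above its median
- logit P(event) = c + ln(OR)·S, with no OSA term, c set to give the event rate, and OR = 1.5, 2 or 3 per SD

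Share of simulated trials with Fisher p ≤ 0.05 (3,000 trials per cell; event rate 25% / 40%):

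| Severity OR per SD | ρ = 0.3 | ρ = 0.5 |
|---|---|---|
| 1.5 | 4% / 5% | 7% / 9% |
| 2 | 7% / 9% | 14% / 18% |
| 3 | 11% / 14% | 28% / 34% |

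The simulation standard error is at most √(0.35 × 0.65 / 3,000) ≈ 0.9 percentage points. Repeat runs differ by about one point, and the rounded ranges are 4-13% at ρ = 0.3 and 8-35% at ρ = 0.5. With ρ = 0, Fisher's test rejects about 3% of the time, since it is conservative here.

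**3. What adjustment buys.** Add a baseline proxy Q = 0.7·S + √(1−0.49)·e′ and test OSA by likelihood ratio in a logistic model. In the worst cell (OR 3, ρ = 0.5, event rate 40%) rejection falls from 35% to about 19% (18% in a repeat of 4,000 trials). The bias is reduced but not removed. In the weakest cells there is little to remove, and the adjusted test sits near its nominal 5%.

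**4. A different mechanism.** Suppose 30% of controls are sicker with 2-3 times the event risk, true OSA prevalence is 30-50% and unrelated to outcome, and 10-50% of the sicker non-OSA patients are labelled OSA (all assumed). The apparent risk ratio is 1.03 to 1.45. Rejection reaches at most 17% at a 25% event rate and 43% at 50%.

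**5. Controls without a recording.** Let a fraction f of patients with events have the event before the recording and so lack OSA status. Let P be the event rate and π the OSA prevalence, with no OSA effect and early events equally likely in both groups.
- Left out: the risk in each group is P(1−f)/(1−fP), so the risk ratio is 1.00.
- Counted as non-OSA: the non-OSA risk becomes [(1−π)P + πfP] / [(1−π) + πfP]. With P = 0.25, f = 0.25, π = 0.5, this is 0.156/0.531 = 0.294, against 0.1875/0.9375 = 0.200 in OSA, a risk ratio of 0.68. Over f = 10-50%, π = 30-50% and P = 25-50% the range is 0.93 to 0.43.

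On the size of f: with an even hazard over 14 days, the first one to three days hold 1/14 = 7% to 3/14 = 21% of events.

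**The case against.** The strongest reply is that severity marking is an inference. The documents give no scoring rule for the recording, so nobody can say from them how far acute COVID shifts the OSA label. Enrolled patients are well enough to go home, which narrows the severity range. That stands, and it is why the figures above are illustrations. At a severity odds ratio of 1.5 and correlation 0.3 there is no material inflation.

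A second reply is that the Protocol already intends to separate OSA from obesity. It does, but the SAP supplies no model for it, and neither document names illness severity as a confounder.

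Third, the comparison is exploratory and confined to one arm. That is correct and limits the importance of the point.

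A reader might also infer more than the documents support:
- **That early admissions leave a serious hole in the comparison.** If 25-50% of events preceded the recording, power for the doubled risk would fall from 41% to 26-36%. That share is assumed and looks high, given same-day to 48-hour delivery, 14-day follow-up, and an Introduction that describes decompensation as late (though it counts from symptom onset, and enrollees are already symptomatic). Only admission or death prevents a recording. Leaving these patients out does not bias a null comparison if early events are equally likely in both groups.
- **That an ED visit before the recording is in the wrong order.** If the target is long-standing OSA, measuring it a day later does not mean that it began later. The order matters only if the exposure is taken to be sleep-disordered breathing during the acute illness.

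**Conclusion.** The point holds as a mismatch between aim and analysis. An unadjusted Fisher test cannot deliver the independent effects that Aim 2 promises, and a single recording made after randomization during acute illness leaves the comparison open to confounding by severity. The mismatch follows from the documents alone. The size of the confounding does not. Under the stated assumptions the false-positive rate ranges from about nominal (4%) to about 35%, and adjustment for a reasonable baseline proxy takes the top value to about 19%.

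The documents do not support saying that OSA status in this trial is a severity marker as a matter of fact, that a particular false-positive rate applies, or that missing recordings by themselves bias the result. The clear risk from missing recordings is that untested controls are silently counted as non-OSA, which the SAP does not rule out. The randomized comparison of CPAP with control is untouched.

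**What to change.** In SAP Exploratory Analyses:

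1. Replace Fisher's test for OSA with a logistic model in controls (penalized if events are few) containing OSA, BMI or obesity, ED oxygen saturation, whether that reading was taken on supplemental oxygen, and days since symptom onset. BMI is on the Screening Form. Saturation, the oxygen flag and "Number of days since symptom onset" are on the ER Admission Data Form.
2. Leave controls without a valid recording out of the OSA comparison. Do not count them as non-OSA. Report their number and outcomes.
3. Add a sensitivity analysis that counts only events after the recording. It should not be the main analysis, because it discards the early events.
4. Describe the result as an association with sleep-disordered breathing measured during acute COVID.

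A repeat using a chart diagnosis of OSA from before the illness would be useful but is optional. The forms shown have no field for it, so it would need extra abstraction.

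**Cost.** SAP wording and one regression, with no new procedure for items 1 to 4. Five terms with about 25-50 events means 25/5 = 5 to 50/5 = 10 events per term, which is why penalization is offered. Precision falls slightly and residual confounding remains. Protocol section 2.3 also admits people denied entry to the ER, who may have no ED saturation, so the SAP should say how a missing covariate is handled.
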